12.3.3.2. Myocardial Ischemia by SPECT

To assess the reduction in % ischemic myocardium in ABSORB RESOLVE sub-study subjects from pre-procedure to 14 ± 1 month follow-up, and to assess between-group differences in the reduction of % ischemic myocardium between the Absorb BVS and XIENCE arms. Baseline SPECT imaging is not mandated per protocol; this secondary analysis will be performed only on subjects who have an available non-study SPECT and will be used for determination of reduction in % ischemia myocardium from pre-procedure to 14 ± 1 month follow-up.

12.3.3.3. Myocardial Ischemia by SPECT

To assess the extent of myocardial ischemia in ABSORB RESOLVE sub-study subjects who have met the parent ABSORB IV angina secondary endpoint (angina group) in comparison to subjects who have not met the angina secondary endpoint (non-angina group), and to assess between-group differences in the Absorb BVS and XIENCE arms. ABSORB IV angina secondary endpoint is defined in **Section 5.2** of the ABSORB IV portion of the protocol.

12.3.3.4. Myocardial Ischemia by CT.

To compare the effect of revascularization by Absorb BVS versus XIENCE on additional measures of reversible ischemia reduction in a) the immediate post PCI period (within 7 days after the index PCI procedure) and b) at 62 ± 1 month follow-up. For this tertiary objective, myocardial ischemia (for both the target vessel territory and global ischemia) will be evaluated by CT perfusion. Myocardial ischemia measures will include:

- 1) Between group reversible myocardial ischemia at 7 days.
- 2) Within-patient reversible myocardial ischemia change from 7 days to 62 ± 1 month follow-up.
- 3) Rates of myocardial perfusion normalization.
- 4) Reduction in reversible myocardial ischemia by severity class [as classified by none (0%), mild (1-4%), moderate (5-9%) and severe ($\geq 10\%$) ischemic myocardium.
- 5) Rates of residual $\geq 10\%$ ischemic myocardium.

12.3.3.5. Lesion-Specific Ischemia by CT.

To compare the effect of revascularization by Absorb BVS versus XIENCE on measures of target vessel and lesion-specific ischemia reduction in a) the immediate post PCI period (within 7 days after the PCI period) and b) at 62 ± 1 month follow-up. For this tertiary objective(s), target vessel and lesion-specific ischemia will be evaluated by FFR_{CT} . Lesion-specific ischemia measures will include between group (at 7 days and at 62 ± 1 month follow-up) and within – patient (change from 7 days to 62 ± 1 month follow-up):

- 1) Differences in absolute FFR_{CT} value.
- 2) Rate of trans-lesion hyperemic pressure difference normalization (as defined by $\text{FFR}_{\text{CT}} \geq 0.80$).

12.4. ABSORB-RESOLVE Study Population and Clinical Site Participation

The study populations will consist of 370 consecutive consenting adult patients registered in the parent ABSORB IV trial. Site participation will be voluntary. The ABSORB-RESOLVE and parent ABSORB IV study subject enrollment will be simultaneous; that is, the 370 subjects registered in this sub-study will be a part of the ~2600 subjects in the ABSORB IV trial. These subjects will undergo all ABSORB IV scheduled follow-up and assessments in addition to the tests associated with this sub-study.

12.4.1. Selection of Subjects

12.4.1.1. Inclusion Criteria (in addition to standard inclusion criteria from ABSORB IV parent trial):

- 1) Subjects that received only Absorb BVS or XIENCE as per their assigned treatment group.
- 2) Successful and uncomplicated PCI procedure, as defined in the main protocol.
- 3) Provision of informed, written consent for the ischemia substudy.

12.4.1.2. Exclusion Criteria. (The following exclusions are in addition to the general exclusion criteria for the ABSORB IV trial.)

- 1) Atrial fibrillation.
- 2) Contraindication to adenosine. Contraindications include including 2nd or 3rd degree heart block; sick sinus syndrome; long QT syndrome; severe hypotension, severe asthma, severe COPD or bronchodilator-dependent COPD.
- 3) Any condition making it unlikely that the patient will be unable or unwilling to follow all the ischemia substudy procedures.

12.4.2. Test Schedule and Subject Visits

Patients enrolled in the RESOLVE study will not undergo the ABSORB-RESOLVE specific testing in the protocol. Clinical follow-up will continue as per protocol and these patients will remain in full cohort analysis. All related imaging analysis will not be conducted.

12.4.2.1. Baseline CT

- Baseline CT (CT#1) performed after registration/randomization and after PCI but no later than 7 days after implantation of Absorb BVS or XIENCE in all eligible subjects. This test may be performed as an in-patient prior to hospital discharge, or after hospital discharge in a study approved facility.
- For subjects in who the randomized PCI procedure is staged, CT#1 should be performed after the last staged procedure. Other tests, however (SPECT and CT#2) should be performed at a time course based on completion of the first PCI procedure (a similar procedure to clinical follow-up in the main ABSORB IV randomized trial).

12.4.2.2. 14 ± 1 months (i.e. 13-15 months) SPECT

- A 14 ± 1 month SPECT study will be performed for all eligible subjects, except under the following conditions (Figures 12.4.2 a, b):
 - Subjects with stable angina occurring before the 14 ± 1 month SPECT should receive a SPECT exam at the unscheduled visit, if clinically indicated or feasible.

- If SPECT performed at the unscheduled visit shows no evidence of suspected ischemia, the following conditions apply:
 - If the SPECT exam occurred within ≤ 7 months of the index PCI, the 14 ± 1 month SPECT must still be performed.
 - If the SPECT exam occurred > 7 months after the index PCI, the 14 ± 1 month SPECT does not have to be performed; the SPECT performed at unscheduled visit will be analyzed as having met the 14 ± 1 month SPECT requirement.
- If SPECT shows evidence of suspected ischemia at the unscheduled visit, it is strongly recommended that intracoronary angiography (ICA) is performed.
 - If the ICA demonstrates no in-stent restenosis (ISR) and TLR is not performed on all target lesions, the following conditions apply:
 - If the unscheduled visit occurred within ≤ 7 months of the index PCI, the 14 ± 1 month SPECT must still be performed.
 - If the unscheduled visit occurred > 7 months after the index PCI, the 14 ± 1 month SPECT does not have to be performed; the SPECT performed at the unscheduled visit will be analyzed as having met the 14 ± 1 month SPECT requirement.
 - If the ICA demonstrates ISR (QCA diameter stenosis $> 50\%$ as determined by the angiographic core laboratory), the following conditions apply:
 - If TLR is not performed on all target lesions, the 14 ± 1 month SPECT must still be performed.
 - If TLR is performed on all target lesions, or if ISR (QCA diameter stenosis $> 50\%$ as determined by the angiographic core laboratory) in all target lesions is present, the 14 ± 1 month SPECT does not have to be performed; the SPECT performed at the unscheduled visit will be analyzed as having met the 14 ± 1 month SPECT requirement.
- Subjects with severe unstable angina or MI and suspected ISR occurring before the 14 ± 1 month SPECT who can't exercise are not required to undergo SPECT before the unscheduled ICA.
 - If TLR was not performed on all target lesions, a 14 ± 1 month SPECT must still be performed.
 - If TLR is performed on all target lesions, or if ISR (QCA diameter stenosis $> 50\%$ as determined by the angiographic core laboratory) in all target lesions is present, the 14 ± 1 month SPECT does not need to be performed.
- If subjects miss CT#1, they should still undergo the 14 ± 1 month SPECT study.

- All subjects are strongly recommended to discontinue their anti-angina medications (i.e., nitrates, calcium channel blockers, and beta-blockers) 24 hours prior to the SPECT if there are no contraindications to discontinuing. Patients with recurrent angina are not required to discontinue their anti-angina medications.

12.4.2.3. 62 ± 1 month CT

- A 62 ± 1 month CT study will be performed for all eligible subjects, except under the following conditions (Figures 12.4.2.a, c):
 - Subjects with stable angina occurring before the 62 ± 1 month CT study should receive a CT exam at the unscheduled visit, if clinically indicated or feasible. If this event has occurred before 15 months and if SPECT has not yet been performed, this CT may be done on the same day as or within a few days of the SPECT imaging (note: if only one study can be performed in this time period, the SPECT should be given preference). If this event has occurred after 15 months or if SPECT had already been performed, the CT#2 exam should be performed (without SPECT).
 - If the CT performed at the unscheduled visit shows no evidence of suspected ischemia, the following conditions apply:
 - If the CT exam occurred within ≤ 36 months of the index PCI, the 62 ± 1 month CT exam must still be performed.
 - If the CT exam occurred > 36 months after the index PCI, the 62 ± 1 month CT exam does not have to be performed; the CT performed at unscheduled visit will be analyzed as having met the 62 ± 1 month CT requirement.
 - If the CT exam shows evidence of suspected ischemia at the unscheduled visit, it is strongly recommended that the subject undergo intracoronary angiography (ICA).
 - If the ICA demonstrates no in-stent restenosis (ISR) and TLR is not performed on all target lesions, the following conditions apply:
 - If the unscheduled visit occurred within ≤ 36 months of the index PCI, the 62 ± 1 month CT exam must still be performed.
 - If the unscheduled visit occurred > 36 months after the index PCI, the 62 ± 1 month CT exam does not have to be performed; the CT exam performed at the unscheduled visit will be analyzed as having met the 62 ± 1 month CT requirement.
 - If the ICA demonstrates ISR (QCA diameter stenosis $> 50\%$ as determined by the angiographic core laboratory), the following conditions apply:

- If TLR is not performed on all target lesions, the 62 ± 1 month CT exam must still be performed.
- If TLR is performed on all target lesions, or if ISR (QCA diameter stenosis $> 50\%$ as determined by the angiographic core laboratory) in all target lesions is present, the 62 ± 1 month CT exam does not have to be performed; the CT exam performed at the unscheduled visit will be analyzed as having met the 62 ± 1 month CT exam requirement.
- Subjects with severe unstable angina or MI and suspected ISR occurring before the 62 ± 1 month CT exam who can't exercise are not required to undergo the CT exam before the unscheduled ICA.
 - If TLR was not performed on all target lesions, a 62 ± 1 month CT exam must still be performed.
 - If TLR is performed on all target lesions, or if ISR (QCA diameter stenosis $> 50\%$ as determined by the angiographic core laboratory) in all target lesions is present, the 62 ± 1 month CT exam does not need to be performed.
- If subjects miss CT#1, they should still undergo the 62 ± 1 month CT exam study.
- All subjects are strongly recommended to discontinue their anti-angina medications (i.e., nitrates, calcium channel blockers, and beta-blockers) 24 hours prior to the CT exam if there are no contraindications to discontinuing. Patients with recurrent angina are not required to discontinue their anti-angina medications.

Both CT and SPECT should be performed in accordance with standard guidelines and standard protocols. The baseline and 62 ± 1 month CT protocol will be performed under rest and pharmacologic stress conditions. The 14 ± 1 month SPECT will be performed under rest and exercise stress conditions. Complete details regarding the each imaging modality and protocol will be provided in the ABSORB-RESOLVE guidance document provided to all participating sites. All participating ABSORB-RESOLVE sites will be required to submit one non-study SPECT and CT study to the core laboratory for site qualification prior to beginning enrollment.

Figure 12.4.2 a. Sub-study design: Overall Trial Flow

[figure not shown]

Figure 12.4.2 b. Sub-study design: Unscheduled visit to perform SPECT at < 14 months.

[figure not shown]
[figure not shown]
[figure not shown]

Figure 12.4.2 c. Sub-study design: Unscheduled visit to perform CTA/CTP at < 62 months.

12.4.3. Procedural Assessments and Treatment Strategy

In the ABSORB-RESOLVE sub-study, all pre-procedure and post-procedure assessments, coronary lesion selection, treatment strategy and antiplatelet regimens must be followed as described in the ABSORB IV parent trial section.

Patients enrolled in the RESOLVE study will not undergo the ABSORB-RESOLVE specific testing in the protocol. Clinical follow-up will continue as per protocol and these patients will remain in full cohort analysis. All related imaging analysis will not be conducted.

APPENDIX I: ABBREVIATIONS AND ACRONYMS

Please refer to **APPENDIX I** of ABSORB III Protocol ([REDACTED] March 14, 2017) for a complete list of abbreviations and acronyms.

APPENDIX II: DEFINITIONS

Please refer to **Appendix II** of ABSORB III Protocol ([REDACTED], March 14, 2017) for complete list of definitions. New or updated definitions are listed below:

MYOCARDIAL INFARCTION (MI)

Protocol MI Definition: Periprocedural MI definition is modified from Moussa ID, Klein LW, Shah B, Mehran R, Mack MJ, Brilakis ES, Reilly JP, Zoghbi G, Holper E, Stone GW. Consideration of a new definition of clinically relevant myocardial infarction after coronary revascularization: an expert consensus document from the Society for Cardiovascular Angiography and Interventions (SCAI). J Am Coll Cardiol. 2013 Oct 22;62(17):1563-70.

This definition will be used for the primary analysis of ABSORB IV and secondary analysis of ABSORB III.

Classification	Biomarker Criteria	Additional Criteria
Periprocedural – patients with a) stable CAD, or b) silent ischemia, or c) acute coronary syndromes with at least 2 baseline troponin values which remained <ULN, or d) acute coronary syndromes in whom the troponin and/or CK-MB levels were elevated but all returned to <ULN prior to the procedure	Absolute CK-MB rises within 48 hours of the procedure to > 5 x ULN for post-PCI or CK-MB > 10 x ULN for post-CABG	Baseline value* < ULN; see also **
Periprocedural – patients with stable CAD and elevated baseline CK-MB, or acute coronary syndromes in whom at least 2 baseline troponin and CK-MB values were drawn and the most recent troponin and CK-MB values were less than the preceding measures by >25%	Absolute incremental CK-MB rise within 48 hours of the procedure from the most recent CK-MB level by > 5 x ULN for post-PCI or > 10 x ULN for post-CABG	
Periprocedural – patients with elevated baseline CK-MB in whom the biomarker levels have not been shown to be stable or falling as defined above (either because only one CK-MB was measured, or the most recent CK-MB measure in a series was either still increasing or had not decreased by	The CK-MB rises within 48 hours of the procedure by an absolute increment from the most recent CK-MB level of > 5 x ULN for post-PCI or > 10 x ULN for post-CABG plus new ST-segment elevation or depression plus signs consistent with a clinically relevant MI, such as new onset or worsening heart failure or sustained hypotension.	The following must also be present: 1. New ST-segment elevation or depression, 2. Plus signs consistent with a clinically relevant MI, such as new onset or worsening heart failure or sustained hypotension.

>25% from the most recent measure)		
Spontaneous (before or >48 hours after any coronary revascularization procedure)	Troponin >ULN or CK-MB > ULN	One or more of the following must also be present: - Symptoms of ischemia; - ECG changes indicative of new ischemia - (new ST-T changes or new LBBB), - Development of pathological Q waves; - Imaging evidence of a new loss of viable myocardium or a new regional wall motion abnormality

ULN=Upper limits of the local laboratory normal (will be collected from each hospital laboratory prior to study commencement); LBBB=Left Bundle-branch Block * Baseline CKMB value is required before study procedure and presumes a typical rise and fall post procedure to diagnose a peri procedure MI
 
** Whenever at least one baseline and one post procedure CK-MB measure are available in a patient with stable CAD, adjudication of MI will be based solely on these biomarker values. If the patient has stable ischemic heart disease and the baseline CK-MB measure are not available, they will be assumed to be within normal limits and MI will be adjudicated by the CEC solely according to the post procedure CK-MB measures. TROPONINS WILL NOT BE USED TO DIAGNOSE PERI-PROCEDURAL MI.
		

- **Periprocedural MI After PCI:**

The periprocedural period includes the first 48 hours after PCI.

- **Periprocedural MI After CABG:**

The periprocedural period includes the first 48 hours after coronary artery bypass grafting (CABG).

- **Spontaneous MI:**

MI after the periprocedural period may be secondary to late stent complications or progression of native disease. Performance of ECG and angiography supports adjudication to either a target or non-target vessel in most cases.

With the unique issues and pathophysiological mechanisms associated with these later events as well as the documented adverse impact on short and long-term prognosis, a more sensitive definition than for periprocedural MI of any elevation of troponin or CKMB above the 99th percentile of the upper range limit (or ULN if URL is not available) is used. All late events that are not associated with a revascularization procedure will be considered simply as spontaneous.

Myocardial infarctions will also be adjudicated based on the following classification:

- **Q wave MI**

Development of new, pathological Q wave on the ECG (≥ 0.04 seconds in duration and ≥ 1 mm in depth) in ≥ 2 contiguous precordial leads or ≥ 2 adjacent limb leads)

- **Non-Q wave MI**

Those MIs which are not Q-wave MI.

Myocardial infarctions will also be adjudicated as to their relation to the Target Vessel

All infarcts that cannot be clearly attributed to a vessel other than the target vessel will be considered related to the target vessel.

For **Universal** and **WHO MI** definitions, please refer to ABSORB III protocol ([REDACTED], August 16, 2018). These definitions will be used for secondary analysis for ABSORB IV and ABSORB III.

ANGINA

Angina is defined as any angina or angina equivalent symptoms determined by the physician and/or research coordinator after interview of the patient, and as adjudicated by a clinical events committee (CEC).

ADVERSE EVENT [AE]

An adverse event (AE) is any untoward medical occurrence, unintended disease or injury, or untoward clinical signs (including abnormal laboratory findings) in subjects, users or other persons, whether or not related to the investigational medical device.

NOTE 1: This definition includes events related to the investigational medical device or the comparator.

NOTE 2: This definition includes events related to the procedures involved.

NOTE 3: For users or other persons, this definition is restricted to events related to investigational medical devices.

An AE can therefore be any unfavorable and unintended sign (including an abnormal laboratory finding), symptom, or disease temporally associated with the use of a medicinal (investigational) product, whether or not related to the medicinal (investigational) product.

UNANTICIPATED SERIOUS ADVERSE DEVICE EFFECT

Unanticipated serious adverse device effect (USADE) refers to any serious adverse effect on health or safety or any life-threatening problem or death caused by, or associated with, a device, if that effect, problem, or death was not previously identified in nature, severity, or degree of incidence in the investigational plan or application (including a supplementary plan or application), or any other unanticipated serious problem associated with a device that relates to the rights, safety, or welfare of subjects.

SERIOUS ADVERSE EVENT [SAE]

If the AE meets any of the criteria below, it is regarded as serious adverse event (SAE).

a) Led to a death,

- b) Led to a serious deterioration in health that either:
- 1) Resulted in a life-threatening illness or injury, or
 - 2) Resulted in a permanent impairment of a body structure or a body function, or
 - 3) Required in-patient hospitalization or prolongation of existing hospitalization, or
 - 4) Resulted in medical or surgical intervention to prevent life threatening illness or injury or permanent impairment to a body structure or a body function.
- c) Led to fetal distress, fetal death or a congenital abnormality or birth defect.
- d) An important medical event that may not result in death, be life-threatening, or require hospitalization but may be considered serious when, based upon appropriate medical judgment, may jeopardize the subject and/or may require intervention to prevent one of the outcomes listed in this definition.

NOTE 1: This includes device deficiencies that might have led to a serious adverse event if a) suitable action had not been taken or b) intervention had not been made or c) if circumstances had been less fortunate. These are handled under the SAE reporting system.

NOTE 2: A planned hospitalization for pre-existing condition, or a procedure required by the Clinical Investigation Plan, without a serious deterioration in health, is not considered to be a serious adverse event.

DEVICE DEFICIENCY (DD)

Device deficiency (DD) is defined as an inadequacy of a medical device related to its identity, quality, durability, reliability, safety or performance, such as malfunction, misuse or use error and inadequate labeling. This includes the failure of the device to meet its performance specifications or otherwise perform as intended. Note: performance specifications include all claims made in the labeling of the device.

PRODUCT EXPERIENCE (PE)

Product Experience (PE) is defined as any expression of customer concern or dissatisfaction, including adverse events and patient issues that occurred during or after the use of a commercially available medical device.

[figure not shown]

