6.3.1.2 General Exclusion Criteria

1. Any surgery requiring general anesthesia or discontinuation of aspirin and/or an ADP antagonist is planned within 12 months after the procedure.
2. Subject has known hypersensitivity or contraindication to device material and its degradants (everolimus, poly (L-lactide), poly (DL-lactide), lactide, lactic acid) and cobalt, chromium, nickel, platinum, tungsten, acrylic and fluoro polymers that cannot be adequately pre-medicated. Subject has a known contrast sensitivity that cannot be adequately pre-medicated.
3. Subject has known allergic reaction, hypersensitivity or contraindication to aspirin; or to clopidogrel and prasugrel and ticagrelor; or to heparin and bivalirudin, and therefore cannot be adequately treated with study medications.
4. Subject had an acute myocardial infarction (AMI: STEMI or NSTEMI) within 72 hours of the index procedure and both CK and CK-MB have not returned to within normal limits at the time of index procedure; or subject with stable angina or silent ischemia has CK-MB that is greater than normal limits at the time of the index procedure.
5. Subject is currently experiencing clinical symptoms consistent with new onset AMI (STEMI or NSTEMI), such as nitrate-unresponsive prolonged chest pain with ischemic ECG changes.
6. Subject has a cardiac arrhythmia as identified at the time of screening for which at least one of the following criteria is met:²⁸
 - a. Subject requires coumadin or any other agent for chronic oral anticoagulation
 - b. Subject is likely to become hemodynamically unstable due to their arrhythmia
 - c. Subject has poor survival prognosis due to their arrhythmia
7. Subject has a left ventricular ejection fraction (LVEF) < 30% assessed by any quantitative method, including but not limited to echocardiography, MRI, Multiple-Gated Acquisition (MUGA) scan, contrast left ventriculography, PET scan, etc. LVEF may be obtained within 6 months prior to the procedure for subjects with stable CAD. For subjects presenting with ACS, LVEF must be assessed during the index hospitalization (which may include during the index procedure by contrast left ventriculography) but prior to randomization in order to confirm the subject's eligibility.

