APPENDIX II: DEFINITIONS

CLINICAL ENDPOINT DEFINITIONS

DEATH (Per ARC Circulation 2007; 115: 2344-2351)

All deaths are considered cardiac unless an unequivocal non-cardiac cause can be established. Specifically, any unexpected death even in patients with coexisting potentially fatal non-cardiac disease (e.g. cancer, infection) should be classified as cardiac.

Cardiac death (CD):

Any death due to proximate cardiac cause (e.g. MI, low-output failure, fatal arrhythmia), unwitnessed death and death of unknown cause, all procedure related deaths including those related to concomitant treatment.

Vascular death:

Death due to non-coronary vascular causes such as cerebrovascular disease, pulmonary embolism, ruptured aortic aneurysm, dissecting aneurysm, or other vascular cause.

Non-cardiovascular death:

Any death not covered by the above definitions such as death caused by infection, malignancy, sepsis, pulmonary causes, accident, suicide or trauma.

MYOCARDIAL INFARCTION (MI)

Protocol MI Definition

Classification	Biomarker Criteria	Additional Criteria
Periprocedural PCI	CK-MB > 5 x ULN	Baseline value* < ULN; see also **
Periprocedural CABG	CK-MB > 10 x ULN	Baseline value* < ULN; see also **
Spontaneous	Troponin >ULN or CK-MB > ULN	One or more of the following must also be present: - Symptoms of ischemia; - ECG changes indicative of new ischemia - (new ST-T changes or new LBBB), - Development of pathological Q waves; - Imaging evidence of a new loss of viable myocardium or a new regional wall motion abnormality
Reinfarction (not related to a procedure)	If the Troponin or CKMB values are stable or decreasing on 2 consecutive samples > 6 hours, a 20% or greater increase 3 to 12 hours after second sample is required to diagnose recurrent MI.	If biomarkers are increasing or peak not reached then insufficient data to diagnose recurrent MI. In this case at least two of the following three conditions must be present: - ECG changes indicative of new ischemia - (new ST-T changes or new LBBB), - Development of pathological Q waves - Imaging evidence of a new loss of viable myocardium or a new regional wall motion abnormality

ULN=Upper limits of the local laboratory normal (will be collected from each hospital laboratory prior to study commencement);

LBBB=Left Bundle-branch Block

* Baseline CKMB value is required before study procedure and presumes a typical rise and fall post procedure to diagnose a peri procedure MI

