
Inclusion Criteria
	
General Inclusion Criteria
 
 1. Subject must be at least 18 years of age. 2. Subject or a legally authorized representative must provide written Informed Consent prior to any study related procedure, per site requirements. 3. Subject must have evidence of myocardial ischemia (e.g., silent ischemia, stable or unstable angina, non-ST-segment elevation MI (NSTEMI), OR recent ST-segment elevation MI (STEMI). Patients with stable coronary syndromes can be enrolled any time after symptom onset if eligibility criteria are otherwise

	
met. Patients with acute coronary syndrome can be enrolled under the following conditions:
 
a. Unstable angina or NSTEMI within 2 weeks of the index procedure.b. STEMI > 72 hours ≤ 2 weeks prior to the index procedure. 
Note: Subjects with UA or NSTEMI or STEMI occurring > 2 weeks of the index procedure can be included in the trial but should be categorized based on their current angina class.
 
4. Subjects must be suitable for PCI. Subjects with stable angina or silent ischemia and < 70% diameter stenosis must have objective signs of ischemia as determined by one of the following: abnormal stress echocardiogram, nuclear scan, ECG, PET, MRI, and/or fractional flow reserve (FFR).
 
(Note: subject with silent ischemia must have a prior history of typical angina, angina-equivalent symptoms, or atypical angina within the past year to be included in the trial.)
 
5. Subject must be an acceptable candidate for coronary artery bypass graft (CABG) surgery.
 
6. Female subject of childbearing potential who does not plan pregnancy for up to 1 year following the index procedure. For a female subject of childbearing potential a pregnancy test must be performed with negative results known within 7 days prior to the index procedure per site standard.
 
7. Female subject is not breast-feeding at the time of the screening visit and will not be breast-feeding for at least 1 year following the index procedure.
 
8. Subject agrees to not participate in any other investigational or invasive clinical study for a period of 5 years following the index procedure.⁴⁰
 
Angiographic Inclusion Criteria
 
Treatment of up to three de novo lesions in a maximum of two epicardial vessels, with a maximum of two lesions per epicardial

--	---

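### ABSORB IV enrols recent MI, but its protocol MI table omits ABSORB III's reinfarction criterion, so residual marker elevation plus ischemic symptoms after 48 h can be classed as a new MI and enter 30-day TLF

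*Protocol*

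**What the plan says.** **Entry.** General inclusion criterion 3 in the ABSORB IV Protocol Summary admits "Unstable angina or NSTEMI within 2 weeks of the index procedure" and "STEMI > 72 hours ≤ 2 weeks prior to the index procedure". It sets no condition that markers have normalised. ABSORB III was stricter: general exclusion 4 (section 6.3.1.2) removed acute MI within 72 h where "both CK and CK-MB have not returned to within normal limits at the time of index procedure". The footnote to its Table 7.1 also asked for CK and CK-MB below ULN after a recent MI.

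**MI definition, ABSORB IV.** Appendix II of the ABSORB IV part refers to ABSORB III's Appendix II for the full list of definitions and then gives new or updated ones, among them a complete MI table. Of that table it says "This definition will be used for the primary analysis of ABSORB IV and secondary analysis of ABSORB III". Three periprocedural rows cover the first 48 h, two of them for raised baseline markers. The fourth row, "Spontaneous (before or >48 hours after any coronary revascularization procedure"), requires troponin or CK-MB above ULN and at least one of ischemic symptoms, new ECG change, Q waves or imaging evidence. It has no condition on change from an earlier value.

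**MI definition, ABSORB III.** The table in ABSORB III's Appendix II has a further row, Reinfarction (not related to a procedure). If markers are stable or falling, "a 20% or greater increase 3 to 12 hours after second sample is required to diagnose recurrent MI". If they are still rising or have not peaked, two of three findings (ECG, Q waves, imaging) are needed.

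**Route to the endpoint.** Attribution defaults to the treated vessel: "All infarcts that cannot be clearly attributed to a vessel other than the target vessel will be considered related to the target vessel". Target-vessel MI by the Appendix II definition is a component of 30-day TLF (ABSORB IV section 5.1).

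**The concern.** The trial with the wider entry criteria has lost the safeguard that the narrower trial had. The sponsor evidently expects raised markers at the procedure, since one periprocedural row covers baseline CK-MB that is still increasing. Within 48 h those rows require a rise over the last value, and one adds ECG and clinical signs. After 48 h every such condition disappears.

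Take an NSTEMI two days before PCI, ischemic pain on day 3, and a troponin that is falling but above ULN. Nothing new need have happened in the myocardium, yet the Spontaneous row is met.

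Troponin released by the PCI meets the same gap. It is barred from diagnosing periprocedural MI, and the required post-procedure draws are CK and CK-MB (section 7.4.2), but it becomes a sufficient marker after 48 h. Troponin is sought at unscheduled ischemic visits (section 7.6), so a day-3 value may have no post-PCI troponin to be compared with.

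At stake is the specificity of the primary endpoint. False MIs common to both arms add variance and cost power. False MIs unequal between the arms would also bias the comparison.

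**Working it through.** **1. Following one case through the text.**

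| Step | ABSORB III | ABSORB IV |
|---|---|---|
| Recent MI with raised CK/CK-MB at PCI | Largely kept out | Admitted |
| Raised baseline, first 48 h | Special notes | Increment rows |
| Marker above ULN and falling, ischemic symptoms after 48 h | Reinfarction row: 20% re-rise needed | Spontaneous row: met as it stands |
| Vessel unclear | Target vessel | Target vessel |

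The other MI definitions are for secondary analysis only. The Universal Definition asks for a rise and/or fall, so it also accepts a falling troponin. The modified WHO definition (CK at least twice ULN with raised CK-MB, or new Q waves) is not met by residual troponin alone.

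**2. The plan's own power figure.** Inputs from SAP section 1.5.1: one-sided alpha 0.025, margin 0.029, 1287 per arm, Farrington-Manning test, power about 92%. The assumed TLF rate is redacted, so 92% cannot be reproduced independently. It can be inverted, assuming equal true rates p:

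power = Φ[(Δ − 1.96·s0) / s1], with s1 = √[2p(1−p)/n] and s0 computed in the same way from the two rates constrained to differ by Δ.

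At p = 4.82% the constrained rates are 6.66% and 3.76%, s0 = 0.00874 and s1 = 0.00845. Then (0.029 − 1.96 × 0.00874)/0.00845 = 1.405, and Φ(1.405) = 92.0%. Powers of 91.5% to 92.5% correspond to p from 4.9% to 4.7%. An unpooled-variance formula gives p = 5.0%.

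**3. Equal false MIs in both arms (size assumed).** The documents do not give the share of subjects with recent MI or how often the case above arises. If 10%, 20% or 30% enter with recent MI and 5% of those meet the row without a new infarct, the excess is 0.10 × 0.05 = 0.5, 0.20 × 0.05 = 1.0 or 0.30 × 0.05 = 1.5 points.

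| Excess per arm | False events per arm (× 1287) | TLF rate | Power |
|---|---|---|---|
| 0 | 0 | 4.8% | 92.0% |
| 0.5 points | 6.4 | 5.3% | 89.6% |
| 1.0 point | 12.9 | 5.8% | 87.2% |
| 1.5 points | 19.3 | 6.3% | 84.7% |

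With 10% to 30% entering and 2% to 10% of those affected, the excess runs from 0.2 to 3.0 points and power from 91% to 77%.

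Equal false positives hardly move the risk difference. With 1% of non-events misclassified, a true difference of 2.9 points appears as 2.9 × 0.99 = 2.87. The cost is variance.

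**4. Unequal false MIs through angina (conditional).** Section 12.2 gives 30-day angina for XIENCE and Absorb as 12.5% against 5.8% unadjusted, and 11.3% against 7.0% after propensity adjustment. The adjusted gap of 4.3 points is the fairer input. Assume 15% to 35% of subjects have residual elevation and 20% to 50% of angina is tested while markers are raised. The differential is then 0.15 × 4.3 × 0.20 = 0.13 points up to 0.35 × 4.3 × 0.50 = 0.75 points in Absorb's favour. A middle case is 0.25 × 4.3 × 1/3 = 0.36 points. With that bias and a true difference at the margin, one-sided type I error rises from 2.5% to about 5.6%. None of the shares is in the documents.

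**The case against.** **Carry-over.** The reference to ABSORB III's Appendix II could be read as keeping its Reinfarction row, because the source cited for the update concerns periprocedural MI. This stands in part. Replacing the whole table points towards deletion, but the text does not settle it. The sentence "All late events that are not associated with a revascularization procedure will be considered simply as spontaneous" does not settle it either, since ABSORB III has the same sentence beside its Reinfarction row. Two readings of a primary-endpoint definition still need resolving.

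**Adjudication.** The CEC separates anginal from non-anginal symptoms (ABSORB IV section 9.1), and ECG and angiography are expected to settle the vessel in most cases. A reader might infer that any chest pain with residual troponin automatically counts as TLF. The documents do not support that: the symptom must be ischemic, and an event clearly due to another vessel is not target-vessel MI. Judging whether pain is anginal does not, however, test for a marker re-rise. The CEC charter is not in the documents and may hold such a rule.

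**A deliberate choice.** Appendix II explains that late MI is meant to have a more sensitive definition. That justifies a low threshold for new events. It does not justify counting an old event again.

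**Bias.** A reader might infer that less early angina with Absorb would leak into TLF and inflate type I error, to about 8% on the unadjusted angina rates. The documents do not show this. Section 12.2 calls the contrast hypothesis-generating, it crosses two studies, and the adjusted rates are closer. The chain also needs assumed shares, and needs every tested episode to fall after 48 h and be adjudicated as target-vessel MI.

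**Conclusion.** The concern holds as a gap in the wording of the primary-endpoint definition. ABSORB IV admits recent MI, expects raised markers, and has no stated re-rise condition after 48 h, so an event that is not a new infarct can enter 30-day TLF. Such events would also remain in cumulative 1-year TLF.

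The supportable size is a loss of power from 92% to about 90% to 85%. This assumes 0.5 to 1.5 points of false MIs equal between arms, equal true TLF rates, and the back-solved rate of 4.8%. The true frequency cannot be found from the documents. A differential effect is possible, and its direction is plausible, but neither its existence nor its size is established. The 5.6% type I error above is an illustration and not a finding.

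**What to change.** State in ABSORB IV Appendix II that, for events more than 48 h after a procedure in subjects whose last troponin or CK-MB was above ULN, the ABSORB III Reinfarction criterion applies as written. That means a re-rise of at least 20% after stable or falling values, or two of the three ECG, Q-wave and imaging findings if markers are still rising or have not peaked. Do not extend the two-of-three test to missing serial samples. ABSORB III's row does not go that far, and section 7.6 asks only for reasonable efforts to obtain enzymes, so true early device-related MIs could be lost.

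For events already adjudicated, keep the pre-specified rule as primary, because changing a primary definition after events have accrued invites its own bias. Have the CEC flag early spontaneous MIs without a documented re-rise. Pre-specify in the SAP that 30-day and 1-year TLF are also reported under the re-rise rule as a sensitivity analysis.

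The cost is a few lines in Appendix II, the SAP and the CEC charter, and a limited re-review using records already held, including the pre-procedure troponin required in ACS patients. The downside is that some true reinfarctions without serial samples may not qualify in the sensitivity analysis.
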